5.5 Strategies for Recruitment and Retention

The overall target study sample size is 30 subjects, with no targets by gender, race and ethnicity, or age. The medical director will identify and recruit patients who are eligible for the study based on patients that have been evaluated and consented for a robotic anatomic lung resection surgery. The medical director or another member of the attending clinical team involved in this study will approach these patients about the study, and if the patient consents to the study, they will be enrolled. Informed consent will be obtained in the same visit as consent for the surgery is obtained, which may occur 1-30 days prior to surgery, to minimize patient visits.

The time period of 3 months identified in a previous section was based on the historical frequency of such patients being screened at HUP and PPMC as well as an estimate of participation rate.

6 STUDY INTERVENTION

6.1 Study Intervention(s) Administration

6.1.1 *Study Intervention Description*

The device intervention being utilized in this study is a handheld digital IS composed of the following components:

- Disposable mouthpiece and airflow tube, made of biocompatible, non-conductive plastic (PLA, TPU) and/or dental resin (size: 1 in. x 1 in. x 0.5 in), and the following electronics
 - Ported pressure sensor
- Device body, made of biocompatible, non-conductive plastic material (PLA) that encases the following electronics which do not come in contact with the patient (size: 7 in. x 2 in. x 2.5 in)
 - Rechargeable Lithium-Ion battery (an off-the-shelf consumer power bank)
 - Anker Nano Power Bank with Built-in Foldable USB-C Connector, 5,000mAh Portable Charger 22.5W
 - Speaker with an output wattage of up to 2W
 - LED display screen (1.3 in diagonal)
 - Digital signal processing microcontroller
 - Coin vibration motor
 - Momentary push button

- Wiring, coated in non-conductive casing

The study intervention also includes a mobile application that can be downloaded to a portable smart device such as a smartphone or tablet.

The digital IS will be used by the patient for the duration of their postoperative stay, turned on each morning after the patient is awake, and turned off before the patient goes to sleep for the night. When turned on, the device will gently vibrate to prompt users every 15 minutes to remind patients to perform their prescribed breathing exercises.

6.1.2 Dosing and Administration

The device will be administered to the patient in the following manner. When patients are in pre-operative holding, nursing staff will record a baseline measurement of inspiratory volume with the digital IS and facilitate patients linking their device to the mobile app if patients have a compatible smartphone. Following surgery, the attending clinical staff will teach patients how to perform breathing exercises with the digital IS and instruct them regarding the quantity, frequency, and volume of inspiratory breaths (once every ~15 minutes, with an initial target inspiratory volume of at least 500 mL) to complete during their postoperative stay. For patients that are able to download the mobile app, the mobile app will include additional instructional material on how to use the digital IS device that patients can access at any time.

After initial instruction by the attending clinical team, the patient will perform inspiratory breaths with the digital IS device independently throughout their hospital stay. To perform an inspiratory breath, the patient will empty their lungs with a large exhale, put the mouthpiece of the device to their mouth, and take a deep inspiratory breath. While the patient is using the device, they will be prompted for each exercise step by audio and visual cues, and their resulting inspiratory volume will be displayed on the device screen after each breath.

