1.2 Key Roles and Study Governance

Sponsor	Medical Director
N/A, principal investigator-initiated study	[name]
	Division of Thoracic Surgery, Hospital of the University of Pennsylvania
	[name]
	[contact]
	[contact]

- 1.3 Schema

Office (within 1-30 days prior to surgery) - Informed Consent

- Obtain informed consent alongside surgery consent
- (Optional) Obtain patient or family member email address (linked to their Apple ID) to approve access to the Airalux app on their App Store (IOS only)
 - The Airalux app provides guided IS exercise sessions, allows patients and family members to view past IS exercise measurements, and gamifies adherence metrics.

Pulmonary function lab – Spirometry Testing

- Patients will receive spirometry testing at the pulmonary function lab. This is part of routine care. This is not a study intervention.

Pre-op holding (morning of surgery) - Baseline Measurement

- Patients receive the Airalux device and use it to perform a baseline IS measurement
- Research team records the device identification key of the device that the patient is receiving
- (Optional) For patients with the Airalux app, they can sign in to the app with their device identification key.

Post-anesthesia care unit (2-4 hours post-surgery) - Study Intervention Administered

- Patients are instructed to perform IS exercises with their device
- The device will gently vibrate/buzz every 15 minutes to prompt patients to complete an IS exercise
- (Optional) Patients can follow guided exercises on the app if desired

Inpatient hospital floor (0-7 days post-surgery) - Study Intervention Administered, Collection of Endpoints

- Patients are instructed to perform IS exercises with their device throughout their hospital stay
- The device will vibrate every 15 minutes to prompt patients to complete IS exercise
- (Optional) Patients can follow guided exercises on the app if desired
- Patient pulse oximetry data is collected every 4 hours. This is part of routine care. This is not a study intervention.
- Patient pain scores are collected at minimum every 12 hours (at least once per shift). This is part of routine care. This is not a study intervention.

Discharge - Study Ends (conclusion of hospital stay)

- Patients will not be able to use the Airalux device outside of the hospital
- Patients will receive a standard of care incentive spirometer to use at home

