4 STUDY PLAN

4.1 Study Design

We hypothesize that use of the investigational device will have a positive impact on patient incentive spirometry adherence. This is a single-arm, exploratory study that will be conducted at the Hospital of the University of Pennsylvania (HUP) and Penn Presbyterian Medical Center (PPMC). The digital IS utilizes a sensor to measure inspiratory breath volume and flow rates, and this data, as well as the time stamps, are transmitted wirelessly to a secure cloud database and a companion mobile-based app. The IS and app incorporate features to instruct and remind patients about their exercises, which include auditory and visual cues as well as a gentle auditory and haptic reminder to perform exercises. Furthermore, the app has additional features to encourage breathing exercises in the form of gamification strategies, and separate interfaces for patients and medical staff to monitor device usage. All of the features are aimed at improving patients' adherence to incentive spirometry.

Subjects will be recruited from patients undergoing any lung resection surgery performed by [name], [name], and/or [name] at HUP and/or PPMC and for which an incentive spirometer is expected to be used by the patient after their surgery. The target enrollment for the study is 30 subjects. The duration of the subject's participation with the trial will be for their entire postoperative hospital stay up to 1 week postoperatively. At the beginning of the subject's participation, study activities will be focused on informed consent, instruction on use of the digital IS, and obtaining baseline inspiratory volume measurements. Most of the remainder of the subject's participation time will be focused on passive data collection performed by the digital IS.

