8 STUDY ASSESSMENT AND PROCEDURES

8.1 Efficacy Assessments

Study Procedures and Evaluations:

- 1) Patient identification and eligibility screening:
 - a. Once a potential participant is identified as already scheduled for a lung resection surgery, the clinical team will determine whether the patient satisfies the eligibility criteria.
 - b. Any additional eligibility criteria that cannot be identified or evaluated via Penn Charts will be reviewed and confirmed by the clinical team following receipt of signed ICF forms.
- 2) Patient visit and informed consent:
 - a. If any additional eligibility criteria need to be screened due to a lack of information in Penn Charts, the patient will be asked relevant questions after providing necessary informed consent to the clinical team.
 - i. This will take place in the doctor's office that is private. Note that in-patient hospital stay will not be billed to the study as the hospital stay is unrelated to participation in the study.
- 3) Patient spirometry testing at the pulmonary function laboratory
 - a. This is already done as part of routine care. This is not a study intervention. Lab results from spirometry testing will be a secondary endpoint.
- 4) Device intervention during patient visit
 - a. After receiving informed consent, during preoperative holding, the clinical team will give the patient one digital IS, facilitate the download of the companion app onto the patient's personal mobile device if applicable, and obtain a baseline inspiratory volume measurement.
 - b. Post-surgery, the clinical team will teach patients how to perform breathing exercises with the digital IS and instruct them regarding the quantity, frequency, and volume of inspiratory breaths to perform throughout their hospital stay.
 - i. While the digital IS is powered on, an auditory and haptic reminder will occur every 15 minutes to remind the patient to perform their breathing exercises. The patient has full autonomy as to when and how often to use the digital IS. Digital IS usage and inspiratory volume data will be collected by the device whenever it is used by the patient.
 - ii. At minimum twice per day, the clinical team will collect pain scores. This is already done as part of routine care. This is not a study intervention.

- iii. Every 4 hours, the clinical team will record a patient's SpO2. This is already done as part of routine care. This is not a study intervention.

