9.4.2 Analysis of the Primary Efficacy Endpoint(s)

As this is a one-arm study and there are no comparative analyses to be made, all of the primary endpoints will be analyzed to determine the average and standard deviation within the total

patient population. In the event that inspiratory breath data could not be collected or were unreliable because of digital IS power interruptions, mouth obstructions that preclude IS use, or other events that may influence digital IS use or inspiratory breath data collection, data from that day will be excluded for the patient.

9.4.3 *Analysis of the Secondary Endpoint(s)*

No secondary endpoints are dependent on findings of primary endpoints. Average change in blood oxygen saturation and pain scores over time will be calculated across the course of each patient's postoperative stay. The change in volume of inspiratory breaths will also be calculated across the course of each patient's postoperative stay. This will also be evaluated against both the baseline IS measurement taken preoperatively as well as pulmonary function lab results. The average and standard deviation of flow rates and time spent at different flow rates will also be calculated. The time spent below or above the target 200ml/s-800ml/s range will be calculated for each inspiratory breath, and used to measure the percentage of attempted inspiratory breaths that fell within this range. As this is a one-arm study and there are no comparative analyses to be made, all of the secondary endpoints will be analyzed to determine the average and standard deviation within the total patient population.

9.4.4 *Safety Analyses*

Not applicable.

9.4.5 *Baseline Descriptive Statistics*

Not applicable.

9.4.6 *Planned Interim Analyses*

Not applicable.

9.4.7 *Sub-Group Analyses*

Not applicable

9.4.8 *Tabulation of Individual Participant Data*

Individual patient data will be stored with a randomized patient number instead of their name (e.g., 001, 002, etc).

9.4.9 *Exploratory Analyses*

Not applicable.

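### The documents disagree on whether patients are taught the breathing manoeuvre before the preoperative volume is taken; if they are not, the comparison with that baseline mixes recovery with training and effort

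*Combined protocol and SAP*

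**What the plan says.** Three operational descriptions put the baseline first and the teaching second.

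- Section 6.1.2: in pre-operative holding, "nursing staff will record a baseline measurement of inspiratory volume with the digital IS". The next sentence but no earlier one introduces teaching: "Following surgery, the attending clinical staff will teach patients how to perform breathing exercises with the digital IS".
- Section 8.1: step 4a, in preoperative holding, is to hand over the device, help with the app "and obtain a baseline inspiratory volume measurement". Step 4b begins "Post-surgery, the clinical team will teach patients how to perform breathing exercises with the digital IS".
- Section 1.3 (schema), morning of surgery: "Patients receive the Airalux device and use it to perform a baseline IS measurement". No instruction step is shown there; exercise instruction first appears in the post-anesthesia care unit.

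Section 4.1 lists the opening activities in the other order: "informed consent, instruction on use of the digital IS, and obtaining baseline inspiratory volume measurements". The Schedule of Activities (12.1) has a baseline row on the day of surgery but no row for instruction, so it does not settle the matter.

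The baseline is used in section 9.4.3. After planning the change in inspiratory volume over the postoperative stay, it adds: "This will also be evaluated against both the baseline IS measurement taken preoperatively". The same sentence names the pulmonary function lab results as a second reference.

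**The concern.** Inspiratory volume depends on technique and effort. Section 6.1.2 describes a manoeuvre (empty the lungs, then a deep breath through the mouthpiece) that patients are taught and then repeat with the achieved volume shown after each breath. If the reference value comes from a first use before that teaching, the change from baseline contains a learning component as well as recovery of the lung. The secondary objective in section 3 is to assess lung recovery after surgery, and a single-arm study has no control group in which the learning component could be seen.

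The digital IS baseline is the only preoperative value measured on the same device as the postoperative breaths. It cannot be retaken once surgery has happened. If staff are left to choose between 4.1 and the operational sections, practice may also vary between patients and sites.

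**Working it through.** **Order of events.** Sections 6.1.2, 8.1 and 1.3 agree on baseline before surgery and teaching after it. Section 4.1 names instruction before baseline, but as a summary list and not as an explicit sequence. The operational sections are more specific and are what staff would follow, so an untaught baseline is the likelier reading, though not the only one.

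**What is specified for the baseline.** No section states coaching, practice breaths, a number of attempts, or whether the best or the mean is used. Sections 1.3, 6.1.2 and 8.1 speak of one measurement; 4.1 and 6.4 use the plural. The number is open.

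**What is specified for the postoperative breaths.** The initial target is at least 500 mL (6.1.2), and readings of 100.0 mL or less are dropped (9.4.1), so every larger breath stays in. Section 9.4.3 has no best-effort rule. The recorded breaths need not be maximal.

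**Size.** The plan gives no figure to reproduce: no baseline volume, SD or learning effect. It also does not say whether change is a ratio or a difference. For illustration I use the ratio of postoperative to baseline volume.

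- u = fraction by which an untaught baseline falls short of a taught one (assumed)
- s = fraction by which recorded postoperative breaths fall short of full effort (assumed)
- observed ratio = true ratio × (1 − s)/(1 − u)

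Take an assumed taught baseline of 2000 mL and a postoperative full-effort volume of 1400 mL, so true recovery is 1400/2000 = 70%.

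| u | s = 0 | s = 10% | s = 20% |
|---|---|---|---|
| 5% | 1.053 → 73.7% | 0.947 → 66.3% | 0.842 → 58.9% |
| 10% | 1.111 → 77.8% | 1.000 → 70.0% | 0.889 → 62.2% |
| 20% | 1.250 → 87.5% | 1.125 → 78.8% | 1.000 → 70.0% |

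Two cells written out: with u = 20% and s = 0, 1400/1600 = 87.5%; with u = 10% and s = 20%, (1400 × 0.80)/(2000 × 0.90) = 1120/1800 = 62.2%.

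Recovery is overstated when u exceeds s, understated when s exceeds u, and unbiased when they are equal. On the difference scale with s = 0, a true deficit of 600 mL would read 400 mL at u = 10% and 200 mL at u = 20%.

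**The case against.** **The baseline may not be uncoached.** Staff are present when it is taken. The device gives audio and visual prompts at each step while in use, and these may well run at baseline, although 6.1.2 describes them after the postoperative instruction. The consent discussion includes an overview of the device (10.1.1.2), though this may be up to 30 days before surgery and is not described as practice. The postoperative teaching also covers how many breaths, how often and how large, so it need not be the patient's first instruction. This stands in part: the documents do not prove that the baseline is untaught. They also state no teaching before it outside 4.1.

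**There are other comparators.** Section 9.4.3 also uses the pulmonary function lab results and the change within the stay. This stands, and the recovery objective does not rest on the digital IS baseline alone. However, the lab values come from a different instrument and setting. The within-stay change can carry its own practice effect and cannot show return to the preoperative level.

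**The stronger inference.** A reader might conclude that the baseline is too low and recovery therefore overstated. The documents do not support that. They give no learning effect, and routine postoperative breaths averaged without a best-effort rule could cancel or reverse it, as the table shows.

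**Limited consequence.** This is one part of a secondary endpoint, summarised by mean and standard deviation in an exploratory study. That is correct and limits the weight of the point.

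**Conclusion.** The point holds as an inconsistency with a measurement consequence. Section 4.1 conflicts with 1.3, 6.1.2 and 8.1 on whether instruction precedes the baseline. If the operational sections are followed, the only same-device preoperative comparator has no stated teaching, number of attempts or summary value, while the breaths set against it are taught and practised. The comparison then mixes recovery with training and effort.

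Neither the size nor the net direction can be derived. The illustrated range of 58.9% to 87.5% around a true 70% rests wholly on assumed values of u and s and on the choice of a ratio scale. The change is worth making because it is cheap and a baseline cannot be recovered after surgery. Both primary adherence endpoints are unaffected, as is the target of 30 patients, which section 9.2 bases on expected patient numbers.

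**What to change.** 1. Reconcile 1.3, 6.1.2 and 8.1 with 4.1 so that the manoeuvre is taught in pre-op holding before the baseline, with a reminder after surgery. Name who gives it: 6.1.2 assigns the baseline to nursing staff and the teaching to attending clinical staff.
2. State a fixed small number of baseline breaths after that instruction, for example three.
3. In 9.4.3, define one statistic and use it at baseline and on each postoperative day, computed from breaths the device already records, for example the mean of the three largest. State whether change is a ratio or a difference. Three of three breaths at baseline against the three largest of many on a postoperative day still favours the latter somewhat, so the text should say how many breaths each daily value is drawn from and acknowledge this when reporting.

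The cost is wording edits, one instruction task moved earlier, possibly a couple of extra baseline breaths, and a few more minutes in pre-op holding on the morning of surgery. No extra postoperative breaths are needed. Practice during the stay may still raise later volumes, so some training effect remains and should be acknowledged.

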6.2 Preparation/Handling/Storage/Accountability

6.2.1 Acquisition and accountability

Prior to patient enrollment, devices and extra replacement mouthpieces will be delivered to the clinical team, who will distribute the devices to patients during each patient's pre-op holding period. Each patient will receive their own personal device to keep. If a device is deemed to be no longer functional, a replacement device will be produced and delivered. Determinants of functionality will be accuracy of inspiratory breath metrics, and proper function of adherence-promoting systems (reminders, live exercise guidance, data collection and transfer to app) and electronic components of the device (speaker, LED Screen, button, battery). These features will be tested prior to returning or delivering any devices to the clinical team.

6.2.2 Formulation, Appearance, Packaging, and Labeling

The devices will be delivered in a cardboard box with foam packing material to prevent device breakage during delivery and storage. Unused devices will be stored in Room 185 of the 14th floor of the South-Pavilion at HUP and in Room 245B of PPMC. Each individual device with its charger will be packaged in a resealable clear plastic package. No other device set up is required. At patient discharge, mouthpieces will be disposed of, and devices will be recollected and stored in Room 185 of the 14th floor of the South-Pavilion at HUP or in Room 245B of PPMC.

6.2.3 Product Storage and Stability

The device will be stored on a flat surface close to the patient's bedside when not being used. The stability of the device is not anticipated to be of concern throughout the course of this study.

6.2.4 Preparation

The device must be prepared in the following fashion:

- 1) If the device battery is not charged, connect the device to a power cord connected to an external power outlet.
- 2) Turn on the device and, if the patient has downloaded the accompanying app, open the mobile app on smartphone/tablet.
- 3) Ensure strong WiFi connection is active.

6.3 Measures to Minimize Bias: Randomization and Blinding

This is a single-arm exploratory study which will not require participant randomization or blinding.

6.4 Study Intervention Compliance

Adherence to the protocol will largely be verified by assessing timestamped data collected by the digital IS. This data will enable the research team to confirm that baseline inspiratory volume measurements were taken prior to surgery.

Data collected by the digital IS devices will be stored on a private secure cloud-based database. Data not consent forms or linking sets, can be accessed and transferred by the members of the study team who will conduct data analysis. This transfer will be done via PennBox.

6.5 Concomitant Therapy

Not applicable.

6.5.1 Rescue Medicine

Not applicable.

7 STUDY INTERVENTION DISCONTINUATION AND PARTICIPANT DISCONTINUATION/WITHDRAWAL

7.1 Discontinuation of Study Intervention

Discontinuation from protocol specified activities will result in discontinuation from the study. In this situation, the device is the only clinical intervention being utilized with patients. As such, discontinuing the use of the IS device prohibits data collection and renders the patient's data incomplete and therefore useless for analyses. Furthermore, there are no follow ups involved in this study so discontinuation from device intervention prevents collection of metrics associated with secondary endpoints and constitutes a patient's discontinuation from the study.

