1 STUDY SUMMARY

1.1 Synopsis

Title:	Airalux Digital Incentive Spirometer
Short Title:	Digital Incentive Spirometer
Study Description:	This single-arm proof-of-concept research study aims to assess the effect of a digital incentive spirometer (IS) device and a companion mobile-based app on incentive spirometry adherence in patients post-surgery. The digital IS utilizes a sensor to measure inspiratory breaths, and these data are transmitted wirelessly to a secure cloud database. The spirometer and app include a patient reminder system, exercise gamification strategies, progress tracking, and additional features designed to promote patient IS use.
Objectives:	The objective of this study is to evaluate the effect of a digital IS that provides gentle auditory and haptic reminders and exercise guidance on patient adherence to incentive spirometry. Secondarily, this study will evaluate metrics relating to lung function to assess post-surgery lung recovery in patients using the digital IS.
Primary Endpoint:	Total incentive spirometry adherence - Number of inspiratory breath attempts performed with the digital IS per day. Consistency of incentive spirometry adherence throughout postoperative stay - Percent of recorded hours in which at least one inspiratory breath was attempted using the digital IS.
Secondary Endpoints	Quality of inspiratory breaths attempted with the digital IS - quality refers to inspiratory volumes achieved. Blood oxygen saturation - Postoperative SpO2 Pain Scores - Postoperative pain scores will be reported on a scale from 0 (no pain) to 10 (unbearable pain). Pulmonary function testing lab results – preoperative spirometry results from pulmonary function lab

Study Population:	
30 patients (of adult categorization) undergoing anatomic lung resection surgery and receive an incentive spirometer as standard-of-care. No restriction on gender, demographic group, or geographic location.
 
We will be enrolling patients that receive surgery from [name] (Principal Investigator), [name] (Chief of Thoracic Surgery), and/or [name] (Chief of Surgery, PPMC) at the sites listed below.

Phase:	Exploratory

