3 STUDY OBJECTIVES AND ENDPOINTS

OBJECTIVES	ENDPOINTS	JUSTIFICATION FOR ENDPOINTS
Primary		
The primary objective is to evaluate the effect of a multifeatured digital IS and integrated phone app on patient adherence to incentive spirometry. Together the device and app will include the following functions: an auditory and haptic reminder cue, visual and auditory cues to guide exercise completion, exercise gamification, and data tracking and visualization features.	The primary endpoints are totality and consistency of incentive spirometry adherence. Specifically, total adherence is a measure of the number of inspiratory breath attempts performed with the digital IS per day, and the consistency of adherence is a measure of the percent of hours in which at least one inspiratory breath was attempted using the digital IS.	The number and frequency of inspiratory breath attempts with the digital IS will be evaluated to assess patient adherence to incentive spirometry.
Secondary		
The secondary objective is to evaluate metrics relating to lung function to assess post-surgery lung recovery in patients using the digital IS.	The secondary endpoints are postoperative blood oxygen saturation (SpO ₂), postoperative pain scores, preoperative pulmonary function spirometry results, and postoperative inspiratory breath quality. Pain scores will be on a scale from 0 (no pain) to 10 (unbearable pain). Specifically, quality refers to inspiratory volumes achieved over time and the flow rate at which inspiratory breaths were taken.	Blood oxygen saturation, pain scores, preoperative spirometry results, and inspiratory breath quality will be evaluated to assess post-surgery lung recovery in patients using the digital IS.
Tertiary		
The tertiary object is to evaluate patient user experience of the digital IS device.	A tertiary endpoint will be survey responses collected from patients at discharge. Please see attached survey for survey questions.	These will be used to assess user experience of the device and companion app if applicable.

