7.2 Participant Discontinuation/Withdrawal from the Study

Participants are free to withdraw from participation in the study at any time upon request.

An investigator may discontinue or withdraw a participant from the study for the following reasons:

- If the participant meets any of the exclusion criteria (either newly developed or not previously recognized) that precludes further study participation.
- If the participant insists on using the standard of care IS device.

The reason for participant discontinuation or withdrawal from the study will be recorded by the study team. Given that none of the aforementioned reasons constitutes an adverse event, it may be the case that no further reporting is necessary. Subjects who sign the informed consent form but do not receive the digital IS may be replaced. Subjects who sign the informed consent form and receive the digital IS, and subsequently withdraw, or are withdrawn or discontinued from the study, will not be replaced.

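### Device use is the primary outcome, but section 7.1 treats data from patients who stop using the device as unusable, and sections 9.3 and 9.4 settle neither who is analysed nor over which days

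*Combined protocol and SAP*

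**What the plan says.** Section 3 states: "The primary endpoints are totality and consistency of incentive spirometry adherence". The synopsis (1.1) defines the first as "Number of inspiratory breath attempts performed with the digital IS per day" and the second as "Percent of recorded hours in which at least one inspiratory breath was attempted using the digital IS".

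Section 7.1 says that "discontinuing the use of the IS device prohibits data collection" and makes the patient's "data incomplete and therefore useless for analyses"; it also treats stopping the device as leaving the study. Section 7.2 lists, among the grounds on which an investigator may withdraw a patient, "If the participant insists on using the standard of care IS device". Patients who received the device and then "withdraw, or are withdrawn or discontinued from the study, will not be replaced". On documentation, 7.2 says: "The reason for participant discontinuation or withdrawal from the study will be recorded by the study team".

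Section 9.3 says only that the population includes adults. Section 9.4.1 averages daily attempts over the visit or, in a parenthesis, over the days the device was in use, and takes consistency as a percentage of powered-on, recording hours. Section 9.4.2 plans a mean and SD in the whole patient population, a term it does not define, and drops individual days on which data could not be collected or were unreliable. Section 8.1 leaves patients free to decide when and how often to use the device.

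**The concern.** In most trials, stopping the intervention is an event that interferes with measuring the outcome. Here, stopping by choice is itself a poor outcome, because the outcome is use. If an analyst follows 7.1, the reported mean and SD describe only patients who kept using the device. If the analyst follows 9.4.2 read literally, everyone is included. The plan does not say which governs.

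The denominator is a second and independent problem. It affects any patient who leaves the device off for a day, whether or not that patient is recorded as discontinued. Two analysts could obtain different primary results from the same data, both in line with 9.4.1.

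There is no control arm, and the mean and SD are the only planned primary results. Who is counted, and over which days, therefore determines the finding. When stoppers are low users over their stay, the error favours the positive effect hypothesised in section 4.1. Because stoppers who received the device are not replaced, the analysed number can also fall below 30.

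**Working it through.** No figure in the plan can be reproduced on this point. The sample size of 30 (9.2) rests on expected recruitment, and no stopping rate is given. The numbers below are illustrations.

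**Inputs.** N = 30 (9.2). Stay L = 3 days, or 2 as an alternative (synopsis: 2-3 days on average). Assumed: k = 3 or 6 stoppers, so d = k/30 = 0.1 or 0.2; all stop after day 1; r is their day-1 rate divided by the other patients' daily mean m.

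**Dropping stoppers.** The full-stay mean is m[(1 − d) + d·r/L], with days after stopping counted as zero. Dropping stoppers reports m. The overstatement is 1/[(1 − d) + d·r/L] − 1.

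- L = 3, r = 1, k = 3: 1/(0.9 + 0.0333) − 1 = 7.1%; 27 patients analysed.
- L = 3, r = 1, k = 6: 1/(0.8 + 0.0667) − 1 = 15.4%; 24 patients analysed.
- L = 2, r = 1: 1/0.95 − 1 = 5.3% and 1/0.90 − 1 = 11.1%.
- Stopping at once (no attempts): 1/0.9 − 1 = 11.1% and 1/0.8 − 1 = 25.0%.
- L = 3, r = 3: the bracket equals 1, so there is no overstatement.

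The bias therefore depends on stoppers' use over the whole stay being lower than the others'.

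**Days-in-use denominator, attempts per day.** A patient who averages m on two days and leaves the device off on the third scores 2m/2 = m over days in use and 2m/3 over the visit. The ratio is 1.5, or 50% higher. If 6 of 30 patients do this and nobody is recorded as discontinued, the group mean is raised by 1/(0.8 + 0.2 × 2/3) − 1 = 7.1%. So keeping stoppers is not enough if this denominator stays: with r = 1, each day-1 stopper scores m over one day in use, which gives the same 7.1% and 15.4% as dropping them.

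**Consistency.** Assume a patient is active in 60% of powered-on hours on day 1 of 3, then leaves the device off, with H daytime hours each day, all powered on on day 1. As a percentage of recorded hours the score is 0.6H/H = 60%. Over all in-hospital daytime hours it is 0.6H/3H = 20%. A patient who never powers the device on after surgery scores 0/0, for which the plan has no rule.

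**Day exclusions.** Section 9.4.2 removes days when data could not be collected, including through other events that may influence use. Section 7.1 says that stopping prevents data collection. Read together, they could remove days of voluntary non-use as well.

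**The case against.** The strongest reply is that 7.1 is not an analysis-set rule. It explains why stopping the device ends participation, while the analysis section refers to the whole patient population and drops days rather than patients, so it accepts incomplete records. This stands in part. A reader might infer that the plan prescribes a completers-only analysis; the documents do not go that far. What they contain is an unresolved conflict, in which the only sentence about the analysis of stoppers' data calls them unusable.

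Second, freedom over use (8.1) means that low use is not in itself discontinuation, so 7.1 affects only patients treated as discontinued, and there may be none. This stands, and it limits the first problem but not the denominator problem.

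Third, days in use might mean days powered on, or might simply be a gloss on length of visit, since 6.1.1 has the device on every day. On the powered-on reading, a powered-on day without breaths stays in as zero and only powered-off days are lost. Such days are also lost only if 'in use' means at least one breath. A reader might infer that days in use always inflates a stopper's score. It does not: a patient who stops on the last inpatient day has no unused day, and the two scores agree.

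Fourth, a patient who turns to the standard device may still perform spirometry, so zero measures use of this device rather than spirometry in general. This is right, and the endpoint should be described accordingly.

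Finally, the study is exploratory, with no formal hypothesis in 9.1 and no decision threshold. That lowers the stakes but does not remove the need for one defined primary estimate.

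**Conclusion.** The concern holds as an unresolved conflict and an open choice in the primary analysis, and should be fixed before the data are analysed. Section 7.1 points towards leaving stoppers out, 9.3 and 9.4.2 neither confirm nor override it, and 9.4.1 permits a denominator that discards days with the device off. Either route tends to overstate adherence when stoppers use the device less over their stay.

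The direction rests on that condition, and the size is unknown. The 7% and 15% for 3 and 6 stoppers assume stopping after day 1 of a 3-day stay and a day-1 rate equal to the others' daily mean. Day 1 is the day of surgery, so that rate could well differ. These percentages should not be read as an expected bias: the documents give no stopping rate, and zero is possible. The 50% is exact for a patient with the device off on 1 of 3 days when that day leaves the denominator. It is not a statement about the group mean.

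**What to change.** 1. **Analysis set.** In 9.3, define the primary analysis set as all patients who received the digital IS and had surgery. Delete from 7.1 the statement that stoppers' data cannot be used, and reconcile 7.1 with 9.3 and 9.4.
2. **Attempts per day.** Keep data up to stopping. In 9.4.1, delete the days-in-use alternative and use postoperative in-hospital days to discharge or day 7, with one stated convention for the part days of surgery and discharge. Count days not used by choice as zero attempts, and describe the endpoint as use of the digital IS. State that such days are not excluded under 9.4.2, which stays for technical failure and inability to use the device.
3. **Withdrawals.** For patients who become ineligible, or who withdraw on request without agreeing to further data collection, use data up to that point without adding zeros. Honour requests to withdraw data (10.1.4).
4. **Consistency.** Keep percent of recorded hours as defined, state that it describes powered-on time only, and report powered-on hours per patient beside it. State how a patient with no powered-on hours is handled. Add a sensitivity analysis over in-hospital daytime hours, with voluntary powered-off hours counted as non-use.
5. **Reporting.** Give the number of stoppers with reasons, and the completers-only mean as a sensitivity analysis.

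The cost is wording in 7.1, 9.3, 9.4.1 and 9.4.2, and a count of in-hospital days added to the recorded-data list in 10.1.3. Powered-on hours are already needed for 9.4.1, and reasons for stopping are already recorded under 7.2. No extra patients or visits are needed. Reported adherence may be lower.
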